5.8.6 Electrocardiograms and Echocardiograms

For each ECG parameter, the Baseline value, the highest/lowest postbaseline value, final observation, and the corresponding change from Baseline will be summarized for treated patients and untreated patients. The highest/lowest ECG value is the largest change for QT Interval corrected by the Fridericia Correction Formula (QTcF), QRS and PR intervals, highest value for QT, and largest absolute change for heart rate. Frequency tables of patients with potentially clinically significant ECG values will also be generated. The total number of potentially clinically significant values will also be summarized. Potentially clinically significant values can be found in Appendix 1 Table 5.

For each ECHO parameter, including the left ventricular ejection fraction (LVEF) value, Baseline value, final observation, and the corresponding change from Baseline will be summarized for treated patients and untreated patients. Frequency tables of predefined markedly abnormal ECHO values will also be generated. Markedly abnormal values can be found in Appendix I Table 5.

All patient-level values for ECG and ECHO variables will be displayed in a data listing. In addition, values meeting the predefined markedly abnormal criteria will be presented in a data listing. Treatment-emergent abnormalities will be indicated.

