9.3. Patient Exclusion Criteria

A patient who meets any of the following criteria will be excluded from this study.

1. Use of any pharmacologic treatment (other than corticosteroids for DMD) within 12 weeks of study drug administration that might affect muscle strength or function (eg, growth hormone, anabolic steroids).
2. Previous or current treatment with any other experimental treatments within 12 weeks prior to study entry or participation in any other clinical trial within 6 months prior to

study entry. (A patient may be enrolled in a concurrent non-interventional or observational study provided his participation does not interfere with this study.)

3. Major surgery within 3 months of study drug administration or planned major surgery for any time during this study.
4. Presence of other clinically significant illness including significant cardiac, pulmonary, hepatic, renal, hematologic, immunologic, behavioral disease or malignancy.
5. Use of any systemic aminoglycoside antibiotic within 12 weeks of study drug administration or need for use of systemic aminoglycoside antibiotics or statins during the study.
6. Have a left ventricular ejection fraction (LVEF) of <50% based on the screening ECHO or QT interval corrected by Fridericia's formula (QTcF) \geq 450 msec based on the screening ECG.
7. Prior or ongoing medical condition that could, in the Investigator's opinion, adversely affect the safety of the patient, make it unlikely that the course of treatment would be completed, or impair the assessment of study results.
8. Patients who seem unwilling or unable to comply with the study procedures, in the Investigator's opinion, are to be excluded.

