14.8.2. Safety Analysis

Safety analyses will be descriptive in nature. Summary statistics for each parameter at a specific visit, as well as the change from Baseline to that visit, will also be displayed. All safety data will be presented in the data listings.

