14.8.2.5. Echocardiograms

The actual value and change from Baseline to each visit will be summarized for each ECHO for EF.

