6. CHANGES IN PLANNED ANALYSES

6.1. Changes from Clinical Protocol-Planned Analyses

Compared to protocol specified analyses, the changes are made as follows:

- CCI [REDACTED]
- CCI [REDACTED]
- The observed values and changes from baseline for clinical laboratory assessments, vital signs and ECG will only be summarized for baseline, the last visit (final observation) and the highest/lowest values. All clinical laboratory assessments, vital signs and ECG results by visit will be in data listing.
- The untreated patient group is intended to evaluate the natural history of the DMD disease for patients who are not amenable to exon 51 skipping and is not considered eligible as a current control group for eteplirsen treated patients due to the following: 1) only 7 patients not amenable to exon 51 skipping were enrolled as supposed to planned 20 patients in untreated group, 2) untreated patients have much less assessment frequency of adverse events during study, 3) most untreated patients have dropped out the study earlier. Thus, no direct comparison is made between eteplirsen treated patients and untreated patients. No hypothesis test, no p-value and no inferential statistics will be made for comparison of eteplirsen treated patients and untreated patients.
- Due to complexity of identifying an external control dataset, the statistical methods for the identification and use of the external control dataset will not be described in this SAP. No analysis of eteplirsen-treated patients as compared to an external control will be performed.
- If an external control is identified in the future, the analysis results may not be included in the CSR, and may be reported in a standalone report.
- CCI [REDACTED].
- No other changes are planned or made.

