Appendix Table 5. Electrocardiogram and Echocardiogram Abnormalities of Interest

Variable	Units	LLN	ULN	Age Group (years)	Markedly Abnormal Criteria
Heart rate	Beats per minute	60	130		NA
QTcF interval	msec	NA	NA	All	Screening Visit >450
				<12	>480
				≥12	>500
				All	<320 Increase >60 >450 >480 >500
QRS interval	msec	NA	NA	<12	IVCD or any QRS conduction disturbance with a QRS >110 msec
				≥12	IVCD or any QRS conduction disturbance with a QRS >120msec
PR interval	msec	NA	NA	<12	>190
				≥12	>220
Left ventricular ejection fraction	%	NA	NA	All	<55%
Fractional shortening	%	NA	NA	All	<29%

IVCD = intraventricular conduction delay; LLN = lower limit of normal; NA = not applicable; QTcF= QT interval Fridericia corrected; ULN = upper limit of normal

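### SAP 5.8.6 replaces the protocol's by-visit ejection-fraction summary with baseline and final observation only, with no lowest value and no readable declaration, so the LVEF time course and some transient falls are left to listings

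*SAP*

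**What the plan says.** Protocol 14.8.2 sets a general rule for safety parameters: "Summary statistics for each parameter at a specific visit, as well as the change from Baseline to that visit, will also be displayed". Section 14.8.2.5 applies it to echocardiography: "The actual value and change from Baseline to each visit will be summarized for each ECHO for EF". The schedules of events (Protocol Sections 2 and 3) place ECHOs at screening and at Weeks 24, 48, 72 and 96 in both groups.

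SAP 5.8.6 summarises less: "For each ECHO parameter, including the left ventricular ejection fraction (LVEF) value, Baseline value, final observation, and the corresponding change from Baseline". The paragraph just before it treats ECG differently: "For each ECG parameter, the Baseline value, the highest/lowest postbaseline value, final observation, and the corresponding change from Baseline will be summarized". For ECHO the SAP adds an abnormality count: "Frequency tables of predefined markedly abnormal ECHO values will also be generated". Appendix Table 5 sets the criteria at LVEF below 55% and fractional shortening below 29%. SAP 5.8.6 also lists all patient-level ECHO values, and lists the markedly abnormal ones with treatment-emergent abnormalities marked.

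SAP 6.1 gives the departures from the protocol. The relevant readable bullet begins: "The observed values and changes from baseline for clinical laboratory assessments, vital signs and ECG will only be summarized for baseline". It goes on to name the last visit and the highest/lowest values. ECHO is not mentioned, and the list closes by saying there are no further changes. Some bullets in 6.1 are redacted.

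The entry limit in Protocol 9.3 excludes boys who "Have a left ventricular ejection fraction (LVEF) of <50% based on the screening ECHO".

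**The concern.** Safety is the primary objective, ECHO abnormality is a named safety endpoint, and the protocol's introduction describes cardiac muscle as progressively involved in this disease. The untreated boys are enrolled to describe natural history. Both purposes are served by LVEF set against time on study, which the protocol promised and the SAP does not tabulate.

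Three features make this more than a change of layout.

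- ECHO is the only one of the four domains that loses its by-visit summary and gets no extreme-value row in return. Where SAP 5.8.5 means to omit that row (height, weight, ulnar length), it says so; for ECHO it gives no reason.
- The final observation falls at different times for different boys. The treated group's End of Study visit has no ECHO, so, absent an unscheduled one, a treated boy who leaves early contributes his last scheduled ECHO. SAP 6.1 reports that most untreated boys dropped out early.
- Protocol 14.1 says departures from its analyses will be recorded in the SAP. A reader who relies on 6.1 would conclude that the by-visit EF table is still planned.

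**Working it through.** There is no sample size, power or error rate to reproduce here; the safety analyses are descriptive. The check is a comparison of texts, a count of visits and some simple arithmetic.

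**1. Planned and retained summaries**

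| Domain | Protocol | SAP summary of level and change | Named in readable SAP 6.1? |
|---|---|---|---|
| Laboratory | by visit (14.8.2.3) | baseline, highest/lowest, final (5.8.4) | yes |
| Vital signs | by visit (14.8.2.2) | baseline, highest/lowest, final (5.8.5) | yes |
| ECG | by visit (14.8.2.4) | baseline, highest/lowest, final (5.8.6) | yes |
| ECHO (EF) | by visit (14.8.2.5) | baseline, final (5.8.6) | no |

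**2. Visits lost.** There are 4 scheduled post-baseline ECHOs (Weeks 24, 48, 72, 96). For a completer the final observation is Week 96, so 4 − 1 = 3 values, or 3/4 = 75%, enter no summary of level or change. They reach a table only by meeting a markedly abnormal criterion.

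**3. Which falls escape every ECHO table.** A fall below 55% meets the frequency-table criterion. A fall still present at the last ECHO shows in the final change. A fall escapes only if it stays at or above 55%, has recovered by the last ECHO, and is not accompanied by fractional shortening below 29%. For a boy with baseline B, the largest such fall is B − 55 points: 65 − 55 = 10, or 72 − 55 = 17. Both baselines are assumptions.

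Illustration with assumed values, fractional shortening staying at or above 29%: baseline 72%, Week 48 56%, Week 96 68%.
- Tabulated change: 68 − 72 = −4 points.
- Lowest-value change: 56 − 72 = −16 points.
- LVEF flag: 56 is not below 55, so none.

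**4. The below-55% count.** Entry admits LVEF of 50 to 54%, and the criterion carries no stated baseline condition and no change-from-baseline component. An assumed boy at 52% throughout would be counted with zero change. One such boy adds 1/20 = 5 percentage points among about 20 treated boys, or 1/7 = 14 among the 7 untreated. The documents do not say whether any boy entered in that range.

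**5. Rough sizing by simulation.** All inputs are assumed: mean LVEF 65%, within-patient SD 3 or 5 points, mean decline of 0 to 2 points per visit, four post-baseline ECHOs, no dropout.
- The lowest value came before the final visit in 40% to 75% of patients.
- Among patients with a drop of at least 10 points at some visit, 21% to 71% did not show a drop of that size at the final visit.
- Among the same patients, 25% to 97% never went below 55%.

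The last two shares were computed separately. The share meeting both conditions, which is what the tables would miss, was not. Part of each drop is measurement noise: with no true decline, the mean change at the lowest of four values was still −3.07 points (SD 3) and −5.15 points (SD 5).

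**The case against.** The strongest defence is that the SAP keeps more than its continuous summary suggests. The endpoint is the incidence of abnormalities, and a frequency table reports incidence where by-visit means do not. Protocol 14.8.2.5 covered EF only and planned no ECHO abnormality table; the SAP adds one, adds fractional shortening, and extends the summary to every ECHO parameter. Cardiac adverse events are also summarised by standard MedDRA queries (SAP 5.8.3). About 20 treated boys with 4 ECHOs each give about 80 values, all listed. With 7 untreated boys, most of them dropping out, by-visit means would rest on a handful of changing individuals, and the listing shows each boy's course better.

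Most of this stands. It rules out the stronger reading a reader might take from 5.8.6, that on-study LVEF declines vanish from the tables. They do not: falls below 55% and persisting declines are both covered. The ECHO sentence lacks the phrase in the laboratory section that covers all time points, but nothing limits it to the final visit.

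A reader might also infer that the change was certainly never declared. Redacted bullets in 6.1 mean that cannot be established. The bullet that makes exactly this change, however, is readable and names three other domains.

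The defence does not explain why ECHO alone lacks an extreme-value row, and listings are not the summary that the protocol promised.

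**Conclusion.** The concern holds in limited form. The protocol's by-visit EF summary is replaced by baseline and final observation, ECHO gets no lowest post-baseline value, and the readable part of SAP 6.1 does not declare this while stating that nothing else changes.

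The loss is the LVEF time course, three of four post-baseline visits for a completer, together with earlier falls that both stay at or above 55% and recover by the last ECHO. The final observation also pools different follow-up times, and the below-55% count does not separate boys who entered below that level. The visit count and the text comparison come straight from the documents. The individual examples and the simulation rest on assumed values and show only what could be missed, not how often it happened. No hypothesis test is affected. The correction is worth making because safety is the primary objective and the data already exist.

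**What to change.** In SAP 5.8.6:

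1. Restore the protocol's summary of EF and its change from baseline at Weeks 24, 48, 72 and 96, by group, with n at each visit.
2. Add the lowest post-baseline LVEF and its change from baseline, as the other domains have.
3. In the table of LVEF below 55%, show boys already below 55% at baseline separately.

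In SAP 6.1, declare any difference from Protocol 14.8.2.5 that remains.

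The cost is SAP wording and about one extra table from data already collected and centrally read. There are two cautions. By-visit figures for the 7 untreated boys will rest on very few values. The lowest of several noisy readings also lies below baseline on average even when nothing has changed, and more so with more ECHOs, so that row should be read beside the by-visit table and not compared between groups with different follow-up.

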5.8.7 Other Safety Assessments

All physical examination results will be listed.

5.9. Efficacy Analyses

For any efficacy assessment that is taken on 2 consecutive days within a visit (i.e., CCI), the average value will be used. If the assessment is taken only on one day, then the value on that day will be used. A value that is marked as invalid on the eCRF will be considered a missing value.

5.9.1 Analysis of Secondary Efficacy Endpoints (Muscle Biopsy-Based Endpoints)

The analyses of dystrophin protein levels determined by Western blot and dystrophin intensity in muscle biopsy tissue determined by IHC were originally described in a separate muscle biopsy-based endpoints SAP, which was approved on 14 August 2017. The muscle biopsy SAP described both interim and final analyses of biopsy endpoints. However, the interim statistical analysis of muscle biopsy-based endpoints was not performed. A revision of the original muscle biopsy SAP is warranted due to coordinated analyses of all efficacy endpoints for supporting CSR. Thus, this SAP describing statistical methods for analyses of muscle biopsy endpoints will supersede the previous

separate muscle biopsy SAP. The results of muscle biopsy endpoints will be reported separately as an addendum report to the CSR.

Correlation among different types of dystrophin related endpoints listed both in the secondary efficacy endpoints and CCI [REDACTED] may be graphically displayed using scatter plot. The Spearman’s rank correlation coefficients will be calculated if appropriate. The effect of body weight and treatment duration on the dystrophin related endpoints will also be graphically displayed using scatter plot or histogram, if deemed appropriate.

5.9.1.1. Quantity of Dystrophin Protein Expression as Measured by Western Blot

For each time point (Baseline, Week 48 or Week 96), 2 blocks of tissues will be analyzed by Western blot, each with two replicates of gels to determine the dystrophin level (% normal). The block average value from two replicate gels will be computed. The overall average is calculated as the mean of the block average values. The overall average values will be used for all analyses. In the case of only 1 available gel for a block, then that value will be used as the block average value.

For the calculation of average assay value, if there are assay results outside of the limits of quantification, different imputation methods will be used (Table 1). Values less than the lower limit of quantification (LLOQ) will be imputed using one of 3 methods: as 0, as 0.24 (level immediately below the LLOQ), and as the actual measured value. Of them, the main analysis will be based on the actual measured value. Analyses based on other imputation methods will be considered sensitivity analyses.

Table 1: Imputation Method for Values Below the Limits for Western blot

Imputation type	Treat value<=LLOQ as	Analysis type
1	As measured	Main analysis
2	0	Sensitivity analysis
3	0.24	Sensitivity analysis

Dystrophin level (% normal) determined by Western blot will be summarized for baseline and each of the on-treatment timepoints (Week 48 and 96). In addition, change in dystrophin from baseline and the fold change from baseline to each on-treatment timepoints will be summarized. Fold change will be calculated in two ways: (1) calculated for each individual as post-baseline value/ baseline value and summarized using descriptive statistics, (2) calculated as the ratio of the treatment mean value post-baseline/treatment mean value at baseline.

A one-sample permutation test will be used to test the null hypothesis that the mean change from Baseline in dystrophin level is 0. In addition, at the final analysis, a two-

sample permutation test will be used to test the null hypothesis that the mean change from Baseline to Week 96 is the same as the mean change from Baseline to Week 48.

CCI [REDACTED]

[REDACTED]

[REDACTED]

[REDACTED]

[REDACTED]

[REDACTED]

[REDACTED]

5.9.1.2. Change from Baseline to Week 48 and Week 96 in Dystrophin Intensity as Determined by Immunohistochemistry (IHC)

Dystrophin intensity level determined by IHC will be based on the average value for each timepoint (Baseline, Week 48, or Week 96). It will be summarized descriptively for baseline and each of the on-treatment timepoints (Week 48 and 96). In addition, change from Baseline and fold change from Baseline will be summarized descriptively. Fold change will be calculated in two ways: (1) calculated for each individual as post-baseline value/ baseline value and summarized using descriptive statistics, (2) calculated as the ratio of the treatment mean value post-baseline/treatment mean value at baseline. A one-sample permutation test will be used to test the null hypothesis that the mean change from Baseline is 0. In addition, at the final analysis, a two-sample permutation test will be used to test the null hypothesis that the mean change from Baseline to Week 96 is the same as the mean change from Baseline to Week 48.

A patient-level listing will be provided.

CCI [REDACTED]

[REDACTED]

[REDACTED]

CCI [REDACTED]

[REDACTED]

[REDACTED]

CCI [REDACTED]

[REDACTED]

[REDACTED]

[REDACTED]

[REDACTED]

CCI [REDACTED]

[REDACTED]

[REDACTED]

[REDACTED]

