3.1.1 Randomization of Muscle Biopsy Schedule

All eteplirsen-treated patients will have a muscle biopsy performed at Baseline. Additionally, eteplirsen-treated patients will be randomly assigned 1:1 through interactive response technology (IRT) to a second muscle biopsy to be performed at Week 48 or 96. Untreated patients will not have muscle biopsies performed.

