4. GENERAL STATISTICAL METHODS AND CONVENTIONS

4.1. General Methods

Summary statistics will be presented by treatment group, unless stated otherwise. Treatment group refers to patients receiving eteplirsen and patients in the untreated group.

For continuous variables, descriptive statistics will include the number of patients with data to be summarized (n), mean, standard deviation, median, minimum, and maximum.

For categorical/qualitative variables, descriptive statistics will include frequency counts and percentages. The total number of patients in a treatment group will be used as the denominator for percentage calculations, unless stated otherwise.

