4.2. Handling of Missing Data

4.2.1 Imputation of Missing Values

CCI [REDACTED]

[REDACTED]

[REDACTED]

[REDACTED]

[REDACTED]

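### The arithmetic mean of individual dystrophin fold changes tends to exceed 1 even with no effect; a geometric mean ratio would be the better summary

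*SAP*

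**What the plan says.** SAP 5.9.1.1 and 5.9.1.2 define fold change from baseline in two ways. The first is a ratio for each child, "calculated for each individual as post-baseline value/ baseline value and summarized using descriptive statistics". The second is "calculated as the ratio of the treatment mean value post-baseline/treatment mean value at baseline". Neither section names one of them as the main figure.

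SAP 4.1 fixes what is reported for a continuous variable: "descriptive statistics will include the number of patients with data to be summarized (n), mean, standard deviation, median, minimum, and maximum". The readable text plans no geometric mean and no log scale.

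For Western blot, SAP 5.9.1.1 says: "Values less than the lower limit of quantification (LLOQ) will be imputed using one of 3 methods". These are "as 0, as 0.24 (level immediately below the LLOQ), and as the actual measured value". The as-measured version is the main analysis and the other two are sensitivity analyses. The rule acts when the gel results are averaged, and the resulting overall average feeds every analysis. The column heading in Table 1 words the trigger differently: "Treat value<=LLOQ as".

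The hypothesis tests in both sections are permutation tests on mean absolute change, not on fold change. SAP 4.2.1, "Imputation of Missing Values", is redacted, as are parts of 4.8 and 5.9.1.1.

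**The concern.** A ratio of two noisy positive measurements is not symmetric about 1. A child whose baseline happens to read low contributes a large ratio. A child whose baseline happens to read high contributes one that can fall no lower than 0. Averaging the ratios arithmetically does not cancel the two. Here both terms are noisy: the biopsies come from opposite arms (Protocol 11.4.1), and each Western blot value averages a few gels.

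Dystrophin is the secondary endpoint, there are about 10 children per on-treatment week, and the plan does not say which fold-change figure leads. The one most easily quoted could therefore be the one that leans upward.

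Two smaller matters follow from the same definition. If the ratio is repeated with low values set to 0, a child whose baseline gels are all set to 0 has no ratio. And a gel exactly at the quantification limit is handled differently by the text and by Table 1.

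**Working it through.** The plan states no figure for fold change, so there is none to reproduce.

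**Inputs from the documents.** About 20 treated children (SAP 3.3), "randomly assigned 1:1 through interactive response technology (IRT) to a second muscle biopsy" at Week 48 or 96 (SAP 3.1.1), so 20 × 1/2 = 10 per week. Two blocks with two gels each give 4 gels per time point (SAP 5.9.1.1).

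**Assumed inputs.** All CVs and all baseline levels. An LLOQ of 0.25% of normal is inferred from 0.24 being described as the level just below it.

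**Step 1: direction.** Let X be baseline and Y on-treatment, both positive and exchangeable under no effect. Then E[Y/X] = E[(Y/X + X/Y)/2] ≥ 1, with equality only if X = Y always. Example: one child goes from 0.2 to 0.4 and another from 0.4 to 0.2. Mean change is 0 and the ratio of means is 0.6/0.6 = 1.00, but the mean individual fold change is (2 + 0.5)/2 = 1.25.

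**Step 2: size.** With independent lognormal within-child variation, E[Y/X] = 1 + CV². Simulation of 10 children with no effect (200,000 runs, between-child CV 80%) gives:

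| Within-child CV | Expected arithmetic mean | Arithmetic mean > 1 | Expected geometric mean | Expected median | Expected ratio of means |
|---|---|---|---|---|---|
| 10% | 1 + 0.01 = 1.01 | 58% | 1.00 | 1.00 | 1.00 |
| 20% | 1 + 0.04 = 1.04 | 65% | 1.00 | 1.01 | 1.01 |
| 30% | 1 + 0.09 = 1.09 | 71% | 1.01 | 1.01 | 1.01 |
| 50% | 1 + 0.25 = 1.25 | 80% | 1.02 | 1.04 | 1.04 |

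The median and the ratio of means exceed 1 in 50–51% of these runs.

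Adding gel error of CV 20%, averaged over 4 gels, multiplies the expectation by about 1 + 0.04/4 = 1.01. A second simulation (40,000 trials, between-child CV 60%) gave 1.05, 1.10 and 1.26 at within-child CV 20%, 30% and 50%. The arithmetic mean exceeded 1 in 67%, 72% and 81% of trials, the geometric mean in about 50%.

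With a true two-fold rise, the expected arithmetic mean is 2 × 1.09 = 2.18 at CV 30% and 2 × 1.25 = 2.50 at CV 50%.

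**Step 3: dependence on exchangeability.** If instead the on-treatment value has expectation X given baseline X, the expected ratio is exactly 1 (simulated 1.000). The result therefore rests on the baseline carrying error of its own.

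**Step 4: zero imputation, if fold change is repeated under it.** The ratio is undefined when all available baseline gels are set to 0. With between-child CV 60%, within-child CV 30% and gel CV 20%, the chance per child is about 0.79, 0.40 and 0.09 at assumed mean baselines of 0.15, 0.3 and 0.6% of normal. For at least one of 10 children, 1 − (1 − p)^10 gives about 1.00, 0.99 and 0.61.

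**Step 5: the limit itself.** Take baseline gels 0.25, 0.20, 0.18 and 0.15 under zero imputation. Under the text the 0.25 is kept and the average is 0.25/4 = 0.0625. Under the Table 1 heading it becomes 0 and the average is 0. An on-treatment average of 0.50 gives 0.50/0.0625 = 8.0 in the first case and no ratio in the second.

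**The case against.** The strongest reply is that nothing in the plan depends on the mean ratio. SAP 4.1 also gives the median, minimum and maximum, SAP 5.9.1 adds the ratio of means, and the tests use absolute change. At a CV of 10–20% the excess is only 1–4%. All of this stands, and it keeps the point minor. It does not make the arithmetic mean a good summary of ratios when a better one costs nothing.

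A reader might infer more in four ways, none of which the documents support.

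- That the dystrophin tests are biased. They are not, because no test uses fold change.
- That the mean fold change must overstate the effect by a known amount. The direction needs exchangeability, and the size needs a CV that the documents do not give.
- That the plan has no rule for a zero baseline. The readable text does not expressly say that individual fold change is repeated under zero imputation, and a rule may sit in the redacted parts. Since n is reported, an undefined ratio would also show as a smaller n.
- That setting low values to 0 and to 0.24 always brackets the main result. It need not. If two children go from 0.10 to 0.20 and from 0.5 to 0.5, the ratio of means is 0.70/0.60 = 1.17 as measured, 0.5/0.5 = 1.00 with 0, and 0.74/0.74 = 1.00 with 0.24.

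The mismatch at the limit is real, but it touches only the sensitivity analyses. The title of Table 1 refers to values below the limits, which agrees with the text and not with its own column heading.

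**Conclusion.** The point holds as a minor improvement to a descriptive supplement. The plan does produce an arithmetic mean of individual ratios for both dystrophin measures. When baseline and on-treatment values are exchangeable and noisy, with no natural drift over 48 or 96 weeks, the expectation of that mean is above 1. Under a lognormal model the excess is negligible at a within-child CV of 10% (1.01) and becomes material at about 30–50% (1.09–1.25). The planned median and ratio of means and the permutation tests are sound.

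The zero-baseline matter is conditional on fold change being repeated under zero imputation and on no rule standing in redacted text. It concerns Western blot only, since Table 1 does not cover immunofluorescence. The disagreement about a value exactly at the limit is a definite wording error of small effect.

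**What to change.** 1. In SAP 5.9.1.1 and 5.9.1.2, make the geometric mean ratio, with median, minimum and maximum, the summary of individual fold change. The arithmetic mean may stay as a secondary figure but should not lead. Keep the ratio of means.
2. In SAP 5.9.1.1, state that individual fold change is not computed when low values are set to 0, and keep that imputation for absolute change. If a redacted rule already covers a zero baseline, a reference to it is enough.
3. Make the text and the Table 1 heading agree on whether a value equal to the LLOQ is imputed.

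The cost is three short wording changes and minor programming, with no new data. The reported fold change may be slightly less favourable, and one sensitivity output may be given up.

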3.3. Sample Size and Power

Sample size for this study is based upon qualitative considerations; no formal sample size calculations will be performed. Up to 40 patients will be included in this study: approximately 20 patients in the eteplirsen-treated group (those amenable to exon 51 skipping) and up to 20 in the untreated control group (those not amenable to exon 51 skipping).

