4.5. Adjustment for Covariates

Not applicable.

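### The randomised Week 96 versus Week 48 dystrophin comparison is valid, but it uses raw change with no baseline covariate and may give up precision

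*SAP*

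**What the plan says.** Biopsy timing is the only randomised assignment described in the documents. Under SAP 3.1.1, "eteplirsen-treated patients will be randomly assigned 1:1 through interactive response technology (IRT) to a second muscle biopsy" at Week 48 or Week 96. SAP 3.3 plans "approximately 20 patients in the eteplirsen-treated group (those amenable to exon 51 skipping"), so about 10 boys per schedule.

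A baseline value is available for everyone analysed. SAP 3.1.1 states: "All eteplirsen-treated patients will have a muscle biopsy performed at Baseline". The Muscle Biopsy Set in SAP 4.3 requires both the baseline and the on-treatment sample.

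For the comparison between schedules, SAP 5.9.1.1 (Western blot) specifies a two-"sample permutation test will be used to test the null hypothesis that the mean change from Baseline to Week 96 is the same" as that to Week 48. SAP 5.9.1.2 (immunofluorescence) repeats it: "a two-sample permutation test will be used to test the null hypothesis that the mean change from Baseline to Week 96" equals the change to Week 48. Neither section names a covariate, and the whole of SAP 4.5, Adjustment for Covariates, reads "Not applicable".

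Protocol 14.9.2.1 planned only a one-sample test at each time point, so the comparison between schedules was added in the SAP. Protocol 14.1 says that any inferential statistics serve descriptive purposes only.

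**The concern.** A change score does use baseline, but with a slope fixed at 1. If the true regression of on-treatment on baseline dystrophin has another slope, the change score carries avoidable variance. Because the schedule is randomised and baseline is measured before treatment, a baseline-adjusted comparison estimates the same difference, and its slope is set by the data.

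There are reasons to doubt a slope of 1. The second biopsy is taken from the contralateral muscle (Protocol 11.4.1), and each Western blot value averages two tissue blocks (SAP 5.9.1.1). Sampling noise of this kind lowers the correlation between the two measurements, and the change score adds the baseline noise to the outcome. With about 10 boys per schedule, the efficiency of the trial's one randomised contrast is worth a sentence in the plan. SAP 4.5 gives no reason for leaving baseline out.

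**Working it through.** **Stated figures.** There are none to reproduce. Protocol 14.2 and SAP 3.3 make no sample size calculation, and no SD, correlation, effect size or significance level is given for this test.

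**Inputs.** From the documents: N = 20 treated boys, allocated 1:1, so n = 10 per schedule. Assumed: k = SD(baseline)/SD(on-treatment), r = their correlation, a two-sided 5% level, and approximately normal values.

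**Variance per patient**, in units of the on-treatment variance:

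- Raw change: 1 + k² − 2rk
- Baseline-adjusted, large sample: 1 − r²
- Difference: (1 + k² − 2rk) − (1 − r²) = (k − r)²

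In large samples the adjusted estimate is therefore never less precise. The two are equal when r = k, that is, when the slope r/k is 1.

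**Small-sample cost.** Estimating one slope inflates the adjusted variance by about 1 + 1/(N − 4) = 1 + 1/16 = 1.0625. If only 16 boys had paired biopsies, it would be 1 + 1/12 = 1.083.

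**Variance ratio, adjusted/raw (below 1 is a gain):**

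| k | r | Raw | Adjusted | Large-sample ratio | Ratio × 1.0625 |
|---|---|---|---|---|---|
| 1.0 | 0.3 | 1.40 | 0.91 | 0.65 | 0.69 |
| 1.0 | 0.5 | 1.00 | 0.75 | 0.75 | 0.80 |
| 1.0 | 0.7 | 0.60 | 0.51 | 0.85 | 0.90 |
| 1.0 | 0.9 | 0.20 | 0.19 | 0.95 | 1.01 |
| 0.1 | 0.1 | 0.99 | 0.99 | 1.00 | 1.06 |
| 0.1 | 0.5 | 0.91 | 0.75 | 0.82 | 0.88 |
| 0.2 | 0.2 | 0.96 | 0.96 | 1.00 | 1.06 |
| 0.2 | 0.7 | 0.76 | 0.51 | 0.67 | 0.71 |
| 0.3 | 0.5 | 0.79 | 0.75 | 0.95 | 1.01 |

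Over k = 0.1 to 0.3 and r = 0 to 0.5 the last column runs from 0.88 to 1.06.

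**Power** for a difference of one SD of the raw change, by the noncentral t distribution:

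- Raw change: noncentrality √(10/2) = 2.236, 18 df, power 0.56.
- Adjusted, large-sample ratio 0.65 (k = 1, r = 0.3): 2.236/√(0.65 × 1.0625) = 2.691, 17 df, power 0.72.
- Adjusted, ratio 1.0: 2.236/√1.0625 = 2.169, 17 df, power 0.53.

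**Simulation check.** Both permutation tests were simulated with 1,500 trials and 499 permutations each. The adjusted test permuted the schedule labels and recomputed the ANCOVA t statistic. The variance ratio was 0.79 to 0.80 at k = 1, r = 0.5 and 1.06 at k = 0.2, r = 0.2, in line with the formula. Rejection rates under the null were 4.7% to 5.6% across both methods, so both hold their level.

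**The case against.** The strongest reply is that nothing is wrong with the planned test. A permutation test on change is valid under randomisation, it already uses baseline, and replacing it is a preference about efficiency. This stands: neither bias nor type I error is at issue. A reader might infer that the comparison is confounded or invalid because SAP 4.5 names no covariate. The documents do not support that, since timing is randomised.

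A second reply is that baseline dystrophin may barely vary. Protocol 6.1 says the mutations typically prevent dystrophin production, and SAP 5.9.1.1 has three rules for Western blot values below the limit of quantification. If many baselines fall there, the sensitivity imputations of 0 and 0.24 turn them into constants, and the covariate then tells little. This stands for Western blot as a possibility, but the documents report no baseline level or spread. The main analysis keeps measured values, and no quantification-limit rule is given for immunofluorescence intensity.

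A third reply is that the large-sample guarantee does not carry over to 20 boys. This is right: a reader might infer that adjustment can only help, but at this size it can raise the variance by about 6%.

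Finally, the stakes are low, because inference is descriptive and safety is the primary objective. Redacted lines follow the Western blot test and cannot be inspected. SAP 4.5 gives no sign that they contain an adjusted analysis.

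**Conclusion.** The point holds as a possible gain in precision with a small, bounded cost. The randomised contrast is analysed on raw change although every boy in the Muscle Biopsy Set has a baseline value, and no reason is given for omitting it.

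The size depends on k and r, which the documents do not give. With equal SDs and r of 0.3 to 0.7, variance falls by about 10% to 31%. With small baseline spread (k = 0.1 to 0.3, r = 0 to 0.5), the result lies between a 12% fall and a 6% rise.

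A reader might infer that the plan demonstrably loses power. That cannot be shown: the rise from 0.56 to 0.72 belongs to one favourable combination, and power slips to 0.53 if the true slope is 1. This is a worthwhile refinement of a descriptive secondary analysis, of low severity.

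**What to change.** In SAP 4.5, replace the present entry with a statement that the baseline value of the same dystrophin endpoint is the covariate for the Week 96 versus Week 48 comparison. In SAP 5.9.1.1 and 5.9.1.2:

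- Prespecify a baseline-adjusted permutation test, for example Freedman-Lane, or permutation of the schedule labels with the ANCOVA statistic.
- Report the adjusted difference with a 95% CI alongside the raw-change test.
- State, before results are seen, which of the two is main.
- Note that under the Western blot imputations of 0 and 0.24 the covariate may carry little information if many baselines are below the limit of quantification.

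If the sponsor prefers raw change alone, SAP 4.5 should give the reason.

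The cost is a few sentences, minor programming, one degree of freedom, and up to about 6% more variance if estimating the slope gains nothing. No new data are needed.
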